### **1.2. Study Design**

#### **1.2.1. Synopsis of Study Design**

This is a randomized, open-label, non-inferiority, multicenter study of abaloparatide-sMTS compared with abaloparatide-SC for the treatment of postmenopausal women with osteoporosis.

[figure not shown]
The study will consist of a Screening Period (up to 2 months), a Pretreatment Period (1 week), and a Treatment Period (12 months) with a final visit 1 month after the last dose of study drug (Follow-Up/End of Study [EOS] visit). 1 month is defined as 30 days in this study. Thus, subjects will participate in the study for up to 16 months.

Eligible subjects will be randomized in a 1:1 treatment ratio to either abaloparatide-sMTS or abaloparatide-SC using a permuted block randomization scheme. During the Treatment Period, subjects will self-administer study drug once a day for 12 months and visit the study site on Days 1 and 14 and Months 1, 2, 3, 4, 5, 6, 7, 8, 9, 10, 11, 12 and Month 13 for the follow-up visit.

All subjects will be provided calcium and Vitamin D to ensure that their daily intake is 1200 mg/day and 800 IU/day, respectively, or a dose determined by the investigator and agreed by the Sponsor Medical Monitor according to the subject's need.

The study design is presented in [Figure 1](#).

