## **4.6. Safety Analyses**

All safety and tolerability analyses will be conducted using the Safety population, except the summary of TEAE by ADA status, which will be conducted using the Antibody population. Treatment classification will be based on the actual treatment received. Unless otherwise specified, no formal statistical hypothesis testing will be performed for safety endpoints, and the presentations will be based on descriptive summaries. For summaries involving visit, the nominal visit will be used, unless otherwise specified.

The impact of the COVID-19 pandemic and the implementation of a variety of mitigations for study conduct will be reviewed and evaluated carefully for the safety assessment. The pandemic-related protocol deviations including missed or delayed visits, missed safety related tests, use of alternative assessment procedures for visit execution, use of alternative data collection or alternative modalities, use of rescue medications, or non-adherence to the planned course of treatment will be identified. Additional data summaries and analyses addressing the impact of the pandemic may be performed if necessary.

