### **4.6.1. Adverse Events**

All AEs will be coded to SOC and PT using MedDRA Version 24.0.

Analyses of AEs will be performed for those events that are considered to be TEAEs. A TEAE is defined as any AE that was absent (i.e., had not occurred) or had resolved prior to the start of study drug, and which occurred on or after the date of the first dose of study drug and within 30 days of the last dose of study drug; or any AE that started prior to the first dose of study drug, was ongoing after study treatment started, and increased in severity after the start of study drug and within 30 days of the last dose of study drug. AEs with missing onset dates will be handled according to the Conventions for Imputing Missing Dates in [Appendix A](#).

TEAEs reported as unanticipated adverse device effects (UADE) or medical device reports (MDR) are those AEs with “Yes” to all of the following three questions on the AE eCRF: “Serious Event?”, “Was AE related to device?”, and “Would you consider this AE unexpected?”. For North American sites, unanticipated device-related SAEs will be reported as UADE for abaloparatide-sMTS, and will be reported as MDR for subjects on abaloparatide-SC. For European sites, unanticipated device-related SAEs will be reported as UADE for subjects on either abaloparatide-sMTS or abaloparatide-SC.

In any tabulation of TEAEs, a subject contributes only once to the count for a given PT and/or SOC, or for a time period category. For summaries by severity, a subject with multiple occurrences of a TEAE will be represented under the most severe occurrence. For summaries by relationship to study drug, a subject with multiple occurrences of a TEAE will be represented under the most related occurrence.

An overall summary of AEs will be presented by treatment group and overall, including the number and percentage of subjects reporting AEs, TEAEs, study treatment-related TEAEs (with probable or possible relationship to study drug), severe TEAEs, treatment-related severe TEAEs, serious TEAEs, treatment-related serious TEAEs, TEAEs leading to study drug interruption, TEAEs leading to study drug withdrawal, TEAEs leading to discontinuation from study, TEAEs related to the device, and TEAEs resulting in death.

The following summaries will be presented:

- TEAEs by SOC and PT
- TEAEs by SOC, PT, and region (North America, Europe)
- TEAEs by SOC, PT and Maximum Severity (mild, moderate, or severe)

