- TEAEs by SOC, PT and relationship to the study drug (related or not related)
- TEAEs by PT

*Note: which will be sorted in descending order of total number of subjects with the preferred term in the overall column.*

- Treatment-related TEAEs by SOC and PT
- Most Common ( $\geq 5\%$  in either treatment group) TEAEs by SOC and PT
- Severe TEAEs by SOC and PT
- Treatment-related Severe TEAEs by SOC and PT
- Serious TEAEs by SOC and PT
- Treatment-related Serious TEAEs by SOC and PT
- TEAEs leading to study drug withdrawal by SOC and PT
- TEAEs leading to discontinuation from study by SOC and PT
- TEAEs leading to death by SOC and PT
- TEAEs leading to study drug interruption by SOC and PT
- Non-TEAEs by SOC and PT.

SOCs will be sorted in alphabetical order. Within an SOC, AEs will be sorted in descending order of the total number of subjects with the PT in the overall group.

To explore the relationship between TEAEs and the duration of study drug exposure, the incidence of TEAEs by time of onset will be presented for the following categories:  $\leq 1$  month,  $> 1$  to  $\leq 3$  months,  $> 3$  to  $\leq 6$  months,  $> 6$  to  $\leq 9$  months, and  $> 9$  months, by treatment group, SOC, and PT. Subjects with multiple occurrences of an AE within a time period will be counted once in each time period that an onset of the AE occurs.

To evaluate the relationship between TEAEs and antibody status, the incidence of TEAEs will also be summarized by antibody status (ADA-, ADA+/Nab+, ADA+/Nab-, All ADA+, and Overall), SOC, and PT using the Antibody population. A summary of TEAEs by PT and antibody status will also be presented by treatment group, in which TEAEs will be sorted in descending order of total number of subjects with the preferred term.

To explore the effect of the COVID-19 pandemic on reported AEs, summaries of TEAEs by SOC and PT, TEAEs leading to treatment discontinuation, and serious TEAEs will also be presented:

- by AE onset date (AE occurs before 01 March 2020, vs AE occurs on or after 01 March 2020)
- by region (North America and Europe)

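### The TEAE-by-onset table in SAP 4.6.1 uses intervals of about 1, 2, 3, 3 and up to 4 months with no subject-time, so comparison across its columns is confounded by interval width

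*SAP*

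**What the plan says.** SAP 4.6.1 (Adverse Events) introduces the table with its aim: "To explore the relationship between TEAEs and the duration of study drug exposure, the incidence of TEAEs by time of onset will be presented". It lists five onset categories: up to 1 month, over 1 to 3, over 3 to 6, over 6 to 9, and over 9 months, by treatment group, SOC and PT. A subject with repeated events "will be counted once in each time period that an onset of the AE occurs", so each cell reflects subjects with at least one onset in that interval.

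Three other statements fix the interval widths:

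- SAP 1.2.1: "subjects will self-administer study drug once a day for 12 months".
- SAP 1.2.1: "1 month is defined as 30 days in this study".
- SAP 4.6.1 defines a new TEAE as one "which occurred on or after the date of the first dose of study drug and within 30 days of the last dose of study drug".

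On the population, SAP 4.6 says "All safety and tolerability analyses will be conducted using the Safety population", with an exception for summaries by antibody status. For the onset table itself, no denominator, number at risk or subject-time is given for each interval. Exposure-adjusted incidence appears later in SAP 4.6.1, but only by patch type within the sMTS group and over total on-treatment exposure. It is not split by onset interval and does not cover the SC group.

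**The concern.** The table answers its stated question only if its columns can be compared with one another. Their widths differ by a factor of up to four, and plain incidence grows with the time over which events are collected. The trend across columns therefore mixes any real change in risk with the width of the interval. An unchanging risk can look like one that grows with time on drug, and a real fall can look like no change. For a daily product given over 12 months by a new delivery route, the pattern of risk with continued use is a natural safety question, and this is the table planned to explore it.

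**Working it through.** The SAP gives no numerical result for this table, so there is no stated figure to reproduce.

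**Interval widths.** With 30-day months, 360 days of treatment and a 30-day window after the last dose, a completer is followed to about Day 390:

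- up to 1 month: 30 days (w = 1 month)
- over 1 to 3 months: 60 days (w = 2)
- over 3 to 6 months: 90 days (w = 3)
- over 6 to 9 months: 90 days (w = 3)
- over 9 months: 90 days on drug + 30 days after = up to 120 days (w = 4)

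**Constant hazard, no dropout.** The hazard λ per month is an assumption, because the documents give none. The expected cell is 1 − exp(−λw).

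| λ per month | ≤1 | >1–3 | >3–6 | >6–9 | >9 | last ÷ first |
|---|---|---|---|---|---|---|
| 0.01 | 1.00% | 1.98% | 2.96% | 2.96% | 3.92% | 3.94 |
| 0.05 | 4.9% | 9.5% | 13.9% | 13.9% | 18.1% | 3.72 |
| 0.30 | 25.9% | 45.1% | 59.3% | 59.3% | 69.9% | 2.70 |

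**Adding dropout.** Assume a constant dropout hazard δ, set so that a proportion d has stopped by Month 12 (exp(−12δ) = 1 − d), with follow-up ending one month after the last dose. The proportion still followed at month a is S(a) = exp(−δ(a − 1)) for a ≥ 1. On a fixed Safety denominator the cell starting at month a ≥ 1 is S(a) × λ/(λ + δ) × [1 − exp(−(λ + δ)w)]. An at-risk head count divides this by S(a). Last-to-first ratios at λ = 0.01:

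| Dropout by Month 12 | Fixed Safety denominator | At-risk head count |
|---|---|---|
| 10% | 3.61 | 3.87 |
| 20% | 3.27 | 3.80 |
| 30% | 2.93 | 3.72 |
| 50% | 2.22 | 3.52 |

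Example for 50%, last cell: δ = ln 2/12 = 0.0578, S(9) = 0.630, and 0.630 × 0.1476 × 0.237 = 2.21%, against 1.00% in the first cell. Neither denominator removes the width effect.

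**The middle step.** The third and fourth intervals are equally wide. Without dropout the step is flat (2.96% to 2.96%). On a fixed denominator it falls from 2.87% to 2.79% at 10% dropout and from 2.42% to 2.03% at 50%.

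**Risk only while on drug.** The last interval then has an effective width of 3 months. With no dropout the ratios are 1 : 1.99 : 2.97 : 2.97 : 2.97. With 40% dropout on a fixed denominator the last cell is 1.94 times the first.

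**A hazard that halves.** Take 0.02 per month to Month 3 and 0.01 afterwards, with no dropout. The cells are 1.98%, 3.92%, 2.96%, 2.96% and 3.92%. The last equals the second because 2 × 0.02 = 4 × 0.01.

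**Subject-time as denominator.** Subjects with onset divided by subject-years in the interval, at λ = 0.01, gives 12.1, 12.1, 12.0, 12.0 and 11.9 per 100 subject-years; these values held at every dropout level tried. At λ = 0.05 with no dropout it gives 59.4, 57.9, 56.5, 56.5 and 55.2. The small drift arises because a subject counts once per interval while her time keeps accruing. If time stops at the first onset in the interval, the rate is λ throughout: 0.05 × (365.25/30) × 100 = 60.9 per 100 subject-years in every column.

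**The case against.** The table is exploratory, and safety is descriptive unless otherwise specified. Both arms use the same intervals, so width does not distort a comparison of sMTS with SC within a column. The bounds are printed as the category labels, so a careful reader can see that they differ. SAP 4.3.1 summarises duration of exposure by arm in matching categories, and SAP 4.1 plans a Kaplan-Meier plot of time to study withdrawal. From these a reader can recover roughly how many subjects were still on drug when each interval began. By-subject AE listings are also planned. All of this stands and keeps the point minor. It does not supply a rate, and the calculation shows that number at risk alone leaves the ratio at 3.5 or more at λ = 0.01.

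Three stronger readings are tempting, and the documents do not support them:

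- **That women who have left stay in the later denominators.** The SAP names the Safety population generally and is silent on the denominator of this table.
- **That a flat risk must appear as a steady rise, and a falling risk is always hidden.** The middle step is flat or falls slightly. For rare events without dropout, a cell is roughly hazard × width, so a last-interval hazard below a quarter of the first would still show the last cell below the first.
- **That only the last column mixes on-drug and off-drug time.** The 30-day window follows each subject's own last dose, so early discontinuers bring off-drug days into earlier columns too.

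**Conclusion.** The point holds as a minor one. The table is meant to show how TEAEs relate to duration of exposure, but its columns differ in width by up to fourfold and carry no subject-time. Under a constant hazard, the last-to-first ratio without dropout is about 3.9 at 0.01 per month and 2.7 at 0.30. At 0.01 per month it is about 2.2 with 50% dropout on a fixed denominator, and about 3 if risk is confined to time on drug with no dropout. The widths follow from the SAP. The hazards, dropout levels and halving scenario are assumptions chosen to show the range, and dropout is taken as constant and unrelated to onset. A reader might infer that the safety comparison between arms is biased or that the trial's conclusion is affected. Neither follows: the intervals are common to both arms, and the non-inferiority decision uses lumbar spine BMD alone.

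**What to change.** In SAP 4.6.1, keep the planned counts and make these changes:

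- For each interval and arm, add the number at risk at its start and the number of subjects with onset per subject-year at risk in that interval.
- State whether time after a subject's first onset within an interval is censored. Censoring removes the small downward drift shown above.
- Show events and time after each subject's own last dose, up to 30 days, as a separate post-treatment category, so that the five intervals hold on-drug time only.
- State the denominator of any percentage that is kept.

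The cost is SAP wording, one derived denominator per interval and a somewhat larger table. No new data are needed.

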### **4.3. Exposure to Study Drug**

#### **4.3.1. Extent of Exposure and Treatment Compliance**

Subjects were trained by study personnel on how to self-administer study drug with the abaloparatide-SC injection pen or the abaloparatide-sMTS patch. On the days of study site visits, study drug must be administered at the study site to accommodate pre-administration and post-administration procedures.

The overall duration of study drug exposure will be calculated using the data recorded on the eCRF as follows:

- Overall duration of study drug exposure (days) = (date of last dose – date of first dose) + 1.

If the date of last dose is missing, then the earlier of the following 2 dates will be used as the last dose date for analysis and summary purposes: the final visit/early termination visit date or the last drug dispense date + 30 days.

For the abaloparatide-SC group, the total number of doses delivered and study drug administration compliance will be calculated in two ways as follows:

- **Based on missed doses in subject diary:**
  - Number of doses delivered = Overall duration of study drug exposure – Total number of missed doses per subject diary
  - Percent compliance (%) to study drug administration =  $(\text{Number of doses delivered} / \text{Overall duration of study drug exposure}) \times 100\%$
- **Based on measurement of drug remaining in pen:**
  - Number of doses delivered =  $[(45.5 \text{ mm} \times \text{Number of used pens}) - \text{Sum of measurements of drug remaining in all used pens}] / 1.08 \text{ mm}$ . Here the 45.5mm is the initial measurement of unused study drug in an unused injection pen and 1.08mm is the distance the plunger travels for each 80 ug dose from the pen.

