All TEAE summaries, including AEs of special interest (AESI, [Section 4.6.2](#)) will be presented by patch type (ultra-low bioburden, sterile) for the abaloparatide-sMTS group. The exposure-adjusted incidence rate of TEAEs will also be presented by patch type for the abaloparatide-sMTS group. The exposure-adjusted incidence rate is calculated as number of subjects with TEAEs divided by the total on-treatment exposure in subject-years.

The number of subjects with any TEAEs, the number of subjects with any SAEs, and the number of subjects with TEAEs leading to study drug withdrawal will also be summarized by treatment group, SOC, PT and age group (< 65, 65 - < 75, and  $\geq$  75 years). Similar tables will be provided by treatment group, SOC, PT and BMI group (BMI < 25, 25  $\leq$  BMI < 30, BMI  $\geq$  30). Both summaries by age group and by BMI group will also be presented by patch type (ultra-low bioburden, sterile) for the abaloparatide-sMTS group.

By-subject listings will be provided for all AEs, including an indicator for TEAE/non-TEAE and for patch type (ultra-low bioburden, sterile). Listings will also be provided for deaths, serious TEAEs, TEAEs leading to study drug withdrawal, TEAEs leading to discontinuation from study, AEs of special interest, and severe AEs.

A data listing for COVID-19 related AEs (AE PTs related to COVID-19 using MedDRA Version 24.0) will be prepared by SOC and PT. A listing of subjects who experience an UADE or MDR will be provided from the clinical database.

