## Appendix A. Conventions for Imputing Missing Dates

### 1. Adverse event (AE) start (onset) date imputation

AE start (onset) date is separated into 3 different data fields, including day, month and year. Completely missing AE start date (i.e., missing day, missing month and missing year) will not be imputed. Partial AE start date will be imputed according to treatment start date as follows in a sequential fashion.

- If AE year is missing, then no imputation
- If AE month and day are missing and
  - if AE year < Treatment year then AE month/day = '01JUL'
  - if AE year = Treatment year then AE month/day = treatment start date+1
  - if AE year > Treatment year then AE month/day = '01JAN'
- If AE day is missing and
  - if AE year < Treatment year then AE day = '15'
  - if AE year = Treatment year and
    - if AE month < Treatment month then AE day = '15'
    - if AE month = Treatment month then AE date = treatment start date+1
    - if AE month > Treatment month then AE day = '01'
  - If AE year > Treatment year then AE day = '01'
- If AE start date is still missing after the above imputation and AE end date is non-missing then AE start date = AE end date.
- If AE start date is still missing after the above imputation then count this AE as a treatment-emergent AE.

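### The exposure-adjusted TEAE rate by patch type counts each subject once but keeps counting her exposure after the first event, so for common events it depends on how long the patch type was worn

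*SAP*

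**What the plan says.** SAP Section 4.6.1 defines the rate in one sentence: "The exposure-adjusted incidence rate is calculated as number of subjects with TEAEs divided by the total on-treatment exposure in subject-years". It is presented by patch type (ultra-low bioburden, sterile) for the sMTS group.

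The other relevant rules are these:

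- **Counting.** In any TEAE tabulation "a subject contributes only once to the count for a given PT and/or SOC, or for a time period category" (SAP 4.6.1).
- **Exposure.** The only written formula is "Overall duration of study drug exposure (days) = (date of last dose – date of first dose) + 1" (SAP 4.3.1). Exposure duration is also summarised by patch type, but nothing there or in 4.6.1 ends it at an event.
- **TEAE window.** A new event counts if it "occurred on or after the date of the first dose of study drug and within 30 days of the last dose of study drug" (SAP 4.6.1).
- **Patch order.** Every sMTS subject starts on the ultra-low bioburden patch. Sterile patches, the type intended for commercial use, are dispensed only after bioequivalence is confirmed (SAP 4.3.1).
- **Dates.** When day and month are both missing, Appendix A says "if AE year = Treatment year then AE month/day = treatment start date+1"; a missing day in the treatment-start month is handled the same way. For an AE with no usable date: "If AE start date is still missing after the above imputation then count this AE as a treatment-emergent AE".
- **Listings.** "By-subject listings will be provided for all AEs, including an indicator for TEAE/non-TEAE and for patch type (ultra-low bioburden, sterile)" (SAP 4.6.1).

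**The concern.** Exposure adjustment is meant to make groups with different follow-up comparable. Here, a subject who has had her event can add nothing more to the numerator for that term, yet she keeps adding to the denominator. The result is a cumulative proportion divided by time worn, and for common events it drifts down as wear time lengthens. Two patch types with the same hazard can then show different rates merely because one was worn longer.

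Common events are foreseeable. Protocol Section 7.1.1 has every application-site skin reaction reported as an AE whatever its severity. Any row counting subjects with any TEAE is at least as common as any single term, so the effect is largest there.

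There are two related gaps. The numerator and denominator cover different windows. The SAP also has no written rule for assigning to a patch type an event that spans the switch, starts after the last dose, or has no usable date. At stake is a misleading safety contrast between the development patch and the commercial one.

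**Working it through.** The documents give no numerical TEAE rate, so there is no stated figure to reproduce. The formula can be evaluated directly. All hazards, risks and durations below are assumptions.

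**1. Wear time.** Let L be a constant hazard of first event, the same on both patch types, and T the years on a patch type.

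- L = −ln(1 − one-year risk), which gives 0.051, 0.223, 0.693 and 1.609 per year for risks of 5%, 20%, 50% and 80%.
- SAP rate = (1 − exp(−LT))/T.
- At-risk rate = (1 − exp(−LT)) ÷ [(1 − exp(−LT))/L] = L, whatever T is.

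| One-year risk | SAP rate per year, 9 months worn | SAP rate per year, 3 months worn | Ratio, 3 vs 9 months | Ratio, 0.4 vs 0.6 years | At-risk ratio |
|---|---|---|---|---|---|
| 5% | 0.050 | 0.051 | 1.013 | 1.005 | 1.00 |
| 20% | 0.205 | 0.217 | 1.056 | 1.022 | 1.00 |
| 50% | 0.541 | 0.636 | 1.177 | 1.067 | 1.00 |
| 80% | 0.935 | 1.325 | 1.418 | 1.150 | 1.00 |

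Worked case (80%): (1 − exp(−1.609 × 0.25))/0.25 = 0.3313/0.25 = 1.325; (1 − exp(−1.609 × 0.75))/0.75 = 0.7009/0.75 = 0.935; 1.325/0.935 = 1.42. At equal durations the ratio is 1.00.

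**2. Window mismatch.** If a rare event kept the same hazard off drug for 30 days, the rate for the last patch worn D days would be inflated by (D + 30)/D: 2.00, 1.33, 1.17 and 1.11 for D = 30, 90, 180 and 270. For an 80% one-year risk and D = 90 (360-day year), the factor is (1 − exp(−1.609 × 120/360))/(1 − exp(−1.609 × 90/360)) = 0.415/0.331 = 1.25. These are upper figures. If nothing starts after the last dose, the factor is 1.00.

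**3. Patch order.** Assume no patch effect, 12 months of treatment and a higher hazard in the first 1/12 year. Sterile/ultra-low ratios by month of switch:

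| Hazard per year (early, then later) | Rate | Month 3 | Month 6 | Month 9 | Month 10.8 |
|---|---|---|---|---|---|
| 1, then 0.7 | SAP | 0.75 | 0.94 | 1.14 | 1.27 |
| 1, then 0.7 | At-risk | 0.87 | 0.92 | 0.94 | 0.95 |
| 8, then 1 | SAP | 0.31 | 0.59 | 0.90 | 1.11 |
| 8, then 1 | At-risk | 0.25 | 0.36 | 0.42 | 0.45 |

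The SAP ratio changes direction with the switch month alone. The at-risk ratio does not, but under strong early clustering it lies further from 1.

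**4. Imputed dates.** Under the study-day rule in SAP 3.2, an onset imputed to treatment start + 1 is (start + 1) − start + 1 = Day 2. Such events therefore fall on the ultra-low bioburden patch.

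**The case against.** The case against has real force on consequence:

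- **Size is hypothetical.** The 1.42 needs both a 9:3 month split and an 80% risk. At 0.6 versus 0.4 years, a 50% risk gives only 1.07. This stands.
- **The rate is descriptive and openly defined.** SAP 4.6 plans no formal safety testing unless otherwise specified, and none is specified for this rate. Exposure and TEAE summaries by patch type, including time of onset, sit beside it. This also stands, but those tables give context and no corrected rate.
- **The remedy is imperfect.** In five of the eight order scenarios above, the SAP ratio is nearer 1. It is nearer there only because its duration bias offsets a real change in hazard over time, and the offset shifts with the switch month.
- **A common constant hazard is assumed.** If susceptibility varies (gamma frailty with variance 1, 3 versus 9 months), the at-risk ratio is 1.17 at 50% and 1.33 at 80% one-year risk. The SAP ratio is 1.40 and 2.00, so the fix reduces the dependence without removing it.
- **The side issues are small.** New application-site reactions should rarely begin after application stops. In the time-of-onset table, a subject with repeated events "will be counted once in each time period that an onset of the AE occurs", so an event merely ongoing at the switch has no new onset. The doubt is mainly about intensity changes, which Protocol 7.1.4 records as separate events. Imputation to Day 2 applies only to some partial dates, and nothing suggests there are many. These are missing details, and the main point does not depend on them.

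**Conclusion.** The concern holds, as a minor point. Followed as written, the rule gives a rate that depends on wear time for common events and combines a 30-day post-dose numerator with an on-treatment denominator.

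Under a shared constant hazard, the wear-time effect is about 1% at a 5% one-year risk. At 80% it reaches 42% for 3 versus 9 months worn. These figures rest on assumed risks and durations. The documents do not report time on each patch, the share of subjects who switched or event risks, so neither size nor direction can be fixed for this trial.

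The primary non-inferiority analysis and the sMTS versus SC comparison are unaffected.

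**What to change.** In SAP Section 4.6.1:

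1. For each term and patch type, report subjects with a first event on that patch type divided by time at risk, from the start of that patch type to the first event or the end of that patch type. The present figure may stay, labelled as a crude rate.
2. Use one window for numerator and denominator. Either leave post-dose onsets out of the rate and show their count, or add the post-dose days to the time at risk.
3. Assign each event to the patch type worn at its original onset. An event ongoing at the switch, or a later intensity-change record of it, is then not a new sterile-patch event. Sterile time at risk for that term begins when the event ends.
4. State how imputed or missing onset dates are handled. One option is to count events whose recorded date cannot place them on one patch type as undetermined and leave them out of the rate.
5. State that sterile always follows ultra-low bioburden in a subject who switches, so early clustering still confounds the comparison and can move the at-risk ratio further from 1 than the crude one. Direct the reader to the time-of-onset table by patch type.

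The cost is a short definition, an assignment rule, a caveat and minor programming. AE records and patch type are already planned for the listings, so no new data are needed. The one downside is that the remaining order confounding becomes more visible.
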